6. STUDY SUBJECT DATA

6.1. Analysis Populations/Sets

The Safety Analysis Set (SAF) includes all randomized subjects who received at least 1 dose of any study drug. The SAF will be conducted on the basis of the treatment assigned and is the basis of analysis summary tables unless otherwise indicated.

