10 STATISTICS

10.1 Analysis Populations

The Full Analysis Set (FAS) includes all subjects who received at least 1 dose of study drug. FAS analyses will be conducted on the basis of the randomized treatment. All efficacy analyses will be assessed using the FAS.

A Per-Protocol Set (PPS) will also be used to analyze efficacy endpoints and will be based on study drug exposure (compliance and/or time on study drug) and major protocol deviations. The criteria for inclusion in the PPS will be finalized and documented in the statistical analysis plan (SAP) prior to database lock.

The Safety Set (SAF) includes all randomized subjects who received at least 1 dose of study drug. The SAF will be conducted on the basis of the actual treatment received. All safety analyses will be assessed using the SAF.

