10.2 Statistical Methods

All statistical analyses will be performed using SAS[®] version 9 or higher.

Phase 1 and Phase 2 will be analyzed separately. Data will be summarized descriptively for Phase 1 by cohort and overall and Phase 2 by Arm and overall. Descriptive summaries for categorical variables will include counts and percentages. Descriptive summaries for continuous variables will include means, medians, standard deviations and minimum and maximum values. Descriptive summaries of time to event data will include median, 25th and 75th percentiles and standard error. Graphical summaries of the data may be presented. All data will be listed for all subjects.

The effects of noncompliance, time to first dose, treatment discontinuations, premature withdrawal from study and covariates will be assessed to determine the impact on the general applicability of results from this study. Further details of the analysis, including the handling of missing data, transformations and other data handling procedures will be provided in the SAP. Exploratory analyses of the data will be conducted as deemed appropriate.

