10.2.2 Analysis of Safety

Safety assessments will occur on all subjects who received any study medication. All safety analyses will be performed for each cohort and overall in Phase 1 and each Arm and overall in Phase 2.

Terminations/premature withdrawals, adverse events, DLTs, vital signs, and laboratory data will be tabulated.

Terminations and premature withdrawals will be summarized by frequency counts and percentages.

Adverse events will be coded to a standard set of terms using the most current version of the Medical Dictionary for Regulatory Activities (MedDRA) dictionary and graded according to NCI CTCAE v4. Adverse events will be listed individually and incidence of adverse events summarized by system organ class and preferred terms within a system organ class. Analysis of toxicity will focus on SAEs and adverse events \geq Grade 3 and attribution to assigned therapy. Administration-site reactions will be listed and tabulated separately from the adverse events.

Changes in vital signs, hematology and clinical chemistry parameters from baseline to the end of the study will be examined. Treatment-emergent changes from normal to abnormal values in key laboratory parameters will be identified. Laboratory data will be summarized for each time point that specimens are collected. Changes in NCI toxicity grading of laboratory data will be presented using shift tables and listings of clinically significant values.

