4. DATA ANALYSIS CONSIDERATIONS

All analyses will be conducted based on SAS 9.3 or higher.

All data in the database will be presented in by-subject data listings.

Unless otherwise stated, all listings will be sorted by subject number and assessment date (and time, if available).

Sponsor: Aduro Biotech, Inc.
Protocol Number: ADU-CL-11
Version and Date: Version 1.0, 03MAY2018

Unless stated otherwise, continuous data will be summarized by Arm and overall within each Phase based on n, mean, median, standard deviation (SD), first quartile (Q1), third quartile (Q3), minimum value, and maximum value.

Unless stated otherwise, categorical data will be summarized by treatment group using n and percentage based on the number of nonmissing values.

- The number of missing values will be presented as a separate category with no percentage, but only if one or more subjects are missing data.
- Counts of zero will be presented without percentages.

Precision

- Mean, Median, Q1, and Q3: one additional decimal place to that reported for Minimum and Maximum
- SD: two additional decimal places than the Minimum and Maximum
- Percentages: reported to one decimal place

No statistical significance test will be performed.

With the exception of missing data handling noted in Section 5.6, data will not be imputed for analysis purposes.

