5. GENERAL DATA HANDLING CONVENTIONS

5.1. Assigned and Actual Treatment

Sponsor: Aduro Biotech, Inc.
 Protocol Number: ADU-CL-11
 Version and Date: Version 1.0, 03MAY2018

All subjects enrolled in the study are assigned to a therapy Arm based on the information in **Table 3**:

Table 3: ADU-CL-11 Treatment Cycles by Arm

| Phase | Arm | Dose ¹ / Route | Treatment Cycle |
|---|----------------------------|---|---|
| 1 | CRS-207/ IDO | CRS-207: 1×10^9 CFU by IV infusion over ~ 1 hour IDO: 100 mg or 300 mg BID Oral | CRS-207: Day 1 of each cycle (Cycles 1-6); Q6W thereafter IDO: BID starting Cycle 1 Day 2 |
| | CRS-207 | CRS-207: 1×10^9 CFU by IV infusion over ~ 1 hour | CRS-207: Day 1 of each cycle (Cycles 1-6); Q6W thereafter |
| 2 | CRS-207/ Pembro/ IDO | Pembro: 200 mg by IV infusion over 30 min CRS-207: 1×10^9 CFU by IV infusion over ~ 1 hour IDO: 300 mg Oral BID ¹ | Pembro: Day 1 of each cycle CRS-207: Day 2 of each cycle (Cycles 1-6); Q6W thereafter IDO: BID starting Cycle 1 Day 3 |
| | CRS-207/ Pembro | Pembro: 200 mg by IV infusion over 30 min CRS-207: 1×10^9 CFU by IV infusion over ~ 1 hour | Pembro: Day 1 of each cycle CRS-207: Day 2 of each cycle (Cycles 1-6); Q6W thereafter |
| BID = twice daily; CFU = colony-forming units; IDO = epacadostat; IV = intravenous; pembro = pembrolizumab; Q6W = once every 6 weeks ¹ RP2D of epacadostat based on Phase 1 dose-evaluation parameters and determined by the SRC; the phase 2 dose may be further adjusted during Phase 2 Safety Run-in | | | |

Phase 2 is a randomized assignment.

Subject data will appear in the column representing the treatment they were assigned during enrollment/randomization, regardless of the treatment actually received.

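### The SAP departs from the protocol's safety analysis on treatment basis, Phase 1 dose columns and DLT tabulation, and Section 9 declares none of it

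*SAP*

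**What the plan says.** **Treatment basis.** Protocol 10.1: "The SAF will be conducted on the basis of the actual treatment received". SAP 6.1: "The SAF will be conducted on the basis of the treatment assigned and is the basis of analysis summary tables unless otherwise indicated". SAP 5.1 repeats the SAP rule for table columns, placing each subject under the assigned treatment "regardless of the treatment actually received".

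**Phase 1 grouping.** Protocol 10.2: "Data will be summarized descriptively for Phase 1 by cohort and overall and Phase 2 by Arm and overall". Protocol 10.2.2 repeats the by-cohort requirement for safety specifically. In SAP 4, "continuous data will be summarized by Arm and overall within each Phase", while categorical data go by treatment group, a term the SAP does not define. The only arm definition in the SAP, Table 3 in Section 5.1, has a single CRS-207/epacadostat row for Phase 1 that covers both 100 mg and 300 mg BID.

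**DLTs.** Protocol 10.2.2: "Terminations/premature withdrawals, adverse events, DLTs, vital signs, and laboratory data will be tabulated". SAP 8.1 places DLTs among the listings. Section 11.2 has Listing 16.2.7.2, and Section 11.1 has no DLT table.

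**Membership.** In SAP 6.1 the Safety Set "includes all randomized subjects who received at least 1 dose of any study drug". Protocol 10.1 also says randomized.

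**Declared changes.** SAP 1 says that changes from the protocol are provided. Section 9 holds one: efficacy endpoints are derived and listed but not summarized.

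**The concern.** A safety table is meant to show what happened to people given a particular regimen. If a subject receives something other than the allocated treatment, an assigned-treatment table shows that subject's toxicity under a regimen she did not get. The protocol chose actual treatment for safety, and the SAP reverses that without saying so.

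The Phase 1 primary objectives are the recommended Phase 2 dose (RP2D) of epacadostat and tolerability, and DLTs head the primary endpoints in SAP 2. A report without dose-cohort columns or a DLT table omits the summary that the protocol requires for those objectives.

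The point has more weight than usual here. Efficacy will not be summarized (SAP 9) and no figures are planned (SAP 11.3), so the safety tables are the main summarized results of the study report synopsis.

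**Working it through.** The point rests on no alpha, power or sample-size figure, so there is no stated number to reproduce. The check is a comparison of the texts, followed by arithmetic for scale.

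**Step 1: the texts side by side**

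| Item | Protocol | SAP | In SAP 9? |
|---|---|---|---|
| Treatment basis for safety | Actual (10.1) | Assigned (5.1, 6.1) | No |
| Phase 1 columns | Cohort and overall (10.2, 10.2.2) | Arm for continuous data; undefined treatment group for categorical data (4) | No |
| DLTs | Tabulated (10.2.2) | Listed only (8.1, 11.2) | No |
| Set membership | Randomized and treated (10.1) | Randomized and treated (6.1) | Not a difference |

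The first and third rows cannot be reconciled by reading. In the second, the SAP does not specify what the protocol requires: SAP 3.1, Table 1, describes the dose cohorts, but no SAP sentence makes them reporting columns, and the table titles in 11.1 do not supply them. SAP 8.1 adds another undefined term, treatment categories, for the exposure-adjusted rates.

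**Step 2: scale of assigned versus actual**

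Inputs: 13 subjects per arm at stage 1 and 27 at full size (Protocol 3.2). With the denominator held fixed, moving one subject with an event in or out of an arm changes the rate by 1/n:

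- n = 13: 1/13 = 7.7 percentage points
- n = 27: 1/27 = 3.7 percentage points

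The documents do not report how many subjects were treated off-assignment. If none were, both bases give the same tables.

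**Step 3: scale if the doses were pooled**

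Inputs: Protocol 1.3.4 reports 4 subjects at 100 mg and 4 at 300 mg as of 3 November 2016, with no DLTs. For an event seen in none of n subjects, the exact one-sided 95% upper bound is 1 − 0.05^(1/n):

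- each dose, 0/4: 1 − 0.05^(1/4) = 52.7%
- pooled, 0/8: 1 − 0.05^(1/8) = 31.2%

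A pooled column would therefore seem to exclude rates that neither dose excludes alone. This shows what is at stake in the column definition. It does not predict a SAP table.

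**Step 4: the shared membership wording**

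Protocol 5.2 says Phase 1 subjects are assigned and Phase 2 subjects are randomized. Assuming 3 to 6 subjects in Dose Cohort 1, 12 in Dose Cohort 2 and 12 on CRS-207 alone, planned Phase 1 enrollment is 3 + 12 + 12 = 27 to 6 + 12 + 12 = 30. Read literally, the word randomized excludes all of them. Yet SAP 11.1 plans Phase 1 tables on the Safety Set, and Protocol 10.2.2 covers everyone who received any study medication. The wording is wrong in both documents and the intent is clear in both.

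**The case against.** The strongest reply has four parts.

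**The SAP may intend dose columns.** A reader might infer that the SAP pools 100 mg and 300 mg. It does not say so. Protocol Table 5 has the same combined row alongside an explicit by-cohort instruction, so the row alone is not evidence of pooling. Treatment group is undefined rather than defined as arm, SAP 3.2 refers to dose levels in Figure 1 (not shown), and SAP 5.1 uses the treatment assigned at enrollment, which in Phase 1 could mean the cohort. This stands: the defensible statement is that the required columns are not specified.

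**The RP2D does not depend on these tables.** A reader might infer that the RP2D question is left without by-dose safety results. The documents do not support that. The Safety Review Committee sets the RP2D from ongoing review (Protocol 3.1), and Phase 2 starts only afterwards (Protocol 3.2). The SAP is dated 3 May 2018, after development ceased on 12 December 2017 (SAP 3.5). By-subject listings of DLTs, adverse events and epacadostat administration remain, so by-dose counts can be recovered. This stands too.

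**The randomized wording is not a SAP departure.** A reader might infer that the SAP contradicts the protocol here, or that Phase 1 tables would really be empty. Neither holds: the protocol uses the same word, and the SAP names many Phase 1 tables on this set.

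**Assigned and actual treatment may coincide.** The study is open-label, study personnel give CRS-207 and pembrolizumab (Protocol 5.5.3), and the documents show no misallocation. That limits the likely effect. It does not remove the contradiction or the need to declare it.

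**Conclusion.** The point holds as three undeclared departures from the protocol's safety analysis: assigned instead of actual treatment, no specified dose-cohort columns for Phase 1, and DLTs listed instead of tabulated. The use of randomized in the Safety Set definition is a separate error common to both documents.

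The numerical effect of the first departure is conditional. It is zero if everyone received the assigned treatment, and up to 7.7 points per misplaced subject in an arm of 13 (3.7 in an arm of 27), with the denominator held fixed. The effect of the second depends on how the columns are programmed. The third is certain from the SAP's own table list: the protocol-required tabulation of a Phase 1 primary endpoint is absent. None of this changes the design, the sample size or the dose decision. It should be corrected because the safety tables carry most of the summarized results and the correction is cheap.

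**What to change.** - **SAP 6.1:** define the Safety Set as everyone given one or more doses of any study drug, in either phase, analysed by treatment actually received. Correct the word randomized in Protocol 10.1 as well, or note the correction in the SAP.
- **SAP 5.1:** use actual treatment for safety columns, and state how a subject whose dose later changes is classified.
- **SAP 4:** replace arm and treatment group with defined columns. Phase 1: CRS-207 alone, each epacadostat dose cohort, and overall. Phase 2: each arm, and overall.
- **SAP 8.1 and 11.1:** add a DLT table by Phase 1 cohort and Phase 2 arm, with its denominator stated. Neither document's analysis-population section defines a DLT-evaluable set.
- **SAP 9:** record any departure that the sponsor decides to keep, with the reason.

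The cost is SAP wording, an actual-treatment variable with some reprogramming, and one small table. No further data collection is needed for the Phase 1 columns or the DLT table, since dosing and DLTs are already listed by subject.

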6.2. Subject Disposition

Sponsor: Aduro Biotech, Inc.
Protocol Number: ADU-CL-11
Version and Date: Version 1.0, 03MAY2018

Summaries of analysis population membership; final study status (ongoing or terminated), including reasons for study termination; treatment status (ongoing or discontinued), including reasons for treatment discontinuation will be produced based on all subjects enrolled in the study. Time on study and duration of treatment will also be summarized.

Screen failures and final subject disposition status will be listed.

6.3. Protocol Deviations

Protocol deviations will be identified and classified as major (violations) before the database is locked. Major protocol deviations may include but are not limited to:

- Violation of Inclusion/Exclusion Criteria
- Dose not properly administered, including
 - Administrations in which protocol-required pre-medication were not administered
- Use of prohibited medications

Protocol deviations will be listed.

6.4. Demographic and Baseline Characteristics

Subject demographics will be summarized for age (years), sex, ethnicity, race, baseline height (cm), baseline weight (kg), BMI (kg/m²), and BSA (m²). Age will also be categorized as a categorical variable (age < 65, ≥ 65 years) for reporting.

The following conversions and equations will be used as applicable:

- Height (in cm) = height (in inches) * 2.54
- Weight (in kg) = weight (in lbs) * 0.4536
- BMI (kg/m²) = weight(kg)/[height(m)²]
- BSA(m²) = $\sqrt{[(\text{height}(\text{cm}) * \text{weight}(\text{kg}))/3600]}$

Duration of time from initial diagnosis to screening (in months); cancer type; histology; genetic mutations; TNM staging at diagnosis; TNM staging at study entry; stage at diagnosis; stage at study entry; disease specific genetic mutations; prior systemic therapy, prior radiation and prior surgery (Yes/No); sum of target lesions per RECIST 1.1 at baseline (mm); baseline CA-125 (and response evaluability per GCIG as Yes/No as identified in Section 7); and baseline ECOG will be summarized. Histology and genetic mutations for phase 1 patients will be provided by Aduro outside of the clinical database.

Subject demographics and baseline characteristics, including cancer related surgeries, systemic therapies, and prior radiotherapy, will be listed.

Sponsor: Aduro Biotech, Inc.
Protocol Number: ADU-CL-11
Version and Date: Version 1.0, 03MAY2018

6.5. Medical History

Medical history will be listed.

6.6. Prior and Concomitant Medication

Concomitant medications will be coded to ATC and preferred name based on the WHO Drug Dictionary (WHO-DDE B2, March 2016). Prior medications are those which have been identified to have been discontinued prior to first study treatment (e.g. taken exclusively during the pre-therapy period). Concomitant medications are those which have been identified to have been taken at any point during the on therapy period.

Prior, concomitant, and post-therapy medications will be presented in data listings; medications which do not occur during the on therapy period will be identified.

6.7. Anticancer Therapies

Anticancer therapies will be coded to ATC and preferred name based on the WHO Drug Dictionary (WHO-DDE B2, March 2016). It is assumed that these therapies will be collected on the associated CRF have been taken following study drug discontinuation in compliance with the protocol. Anticancer therapies will be presented in a data listing.

6.8. Study Drug Exposure and Compliance

The number of cycles of administration (of any dose amount) of pembrolizumab and epacadostat will be reported as a continuous and categorical outcome; categories for reporting will include: < 5 Cycles; 5 - 15 Cycles; > 15 to 25 Cycles; and > 25 Cycles.

The number of infusions of CRS-207 will also be reported as both a continuous and categorical outcome; categories for reporting will be < 5 infusions; 5 – 10 infusions; > 10 to 15 infusions; and > 15 infusions.

For CRS-207, the average volume administered for each infusion (or cycle) will be summarized by therapy. This will be calculated for each subject in (mL / infusion or mL / Cycle):

$(\text{Sum of Total Volume Administered [mL]}) / (\text{Total Number of Administrations})$

The average dose intensity for each pembrolizumab cycle will be summarized. This will be calculated for each subject in (mg / Cycle):

$(\text{Sum of Total Dose Received [mg]}) / (\text{Total Number of Administrations})$

Sponsor: Aduro Biotech, Inc.
Protocol Number: ADU-CL-11
Version and Date: Version 1.0, 03MAY2018

The incidence of infusion interruptions, as well as the total number of interruptions will be displayed for CRS-207 and pembrolizumab separately. Reasons for infusion interruption will also be summarized.

The incidence and number of epacadostat dose reductions will be summarized.

For epacadostat, the mean daily dose will be summarized. This will be calculated for each subject in (mg / Day):

(Sum of Total Doses Received [mg]) / (Duration of epacadostat therapy)

Duration of treatment for each drug, based on similar definitions provided in 5.3, will also be summarized.

Epacadostat dosing, CRS-207 and pembrolizumab administrations, infusion interruptions, and dose reduction information, as well as derived drug exposure metrics, will be listed.

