4.3.2 Epacadostat and Pembrolizumab

If the subject meets eligibility criteria for the study and is assigned or randomized to receive epacadostat BID and/or pembrolizumab, dosing may initiate and should continue per protocol. The Study Medical Monitor will be notified of any dose interruptions due to safety concerns ([Section 5.4.1](#)).

Pembrolizumab dosing may be delayed up to 2 weeks, after which time it will be considered missed and the subject would continue onto the next scheduled dose. If a dose is delayed more than 2 weeks, contact the Sponsor Medical Monitor for further instruction on continued dosing.

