All Other Drug-Related Toxicity	3 or Severe ³	Toxicity resolves to Grade 0-1	Related: Reduce by 1 dose level Not Related: Same dose level	Toxicity does not resolve within 12 weeks of last dose or inability to reduce corticosteroid to 10 mg or less of prednisone or equivalent per day within 12 weeks
	4	Permanently discontinue	n/a	Permanently discontinue

³ Subjects with intolerable or persistent Grade 2 drug-related AE may hold study medication at physician discretion. Permanently discontinue epacadostat for persistent Grade 2 adverse reactions for which treatment with study drug has been held, that do not recover to Grade 0-1 within 12 weeks of the last dose.

Table 7 Pembrolizumab Dose Modification Guidelines for Drug-Related Adverse Events

Toxicity	Hold Treatment For Grade	Timing for Restarting Treatment	Treatment Discontinuation
Diarrhea/Colitis	2-3	Toxicity resolves to Grade 0-1	Toxicity does not resolve within 12 weeks of last dose or inability to reduce corticosteroid to 10 mg or less of prednisone or equivalent per day within 12 weeks
	4	Permanently discontinue	Permanently discontinue
AST, ALT, or Increased Bilirubin	2	Toxicity resolves to Grade 0-1	Toxicity does not resolve within 12 weeks of last dose
	3-4	Permanently discontinue (see exception below) ^a	Permanently discontinue
Type 1 diabetes mellitus (if new onset) or Hyperglycemia	T1DM or 3-4	Hold pembrolizumab for new onset Type 1 diabetes mellitus or Grade 3-4 hyperglycemia associated with evidence of beta cell failure	Resume pembrolizumab when subjects are clinically and metabolically stable
Hypophysitis	2-4	Toxicity resolves to Grade 0-1. Therapy with pembrolizumab can be continued while endocrine replacement therapy is instituted	Toxicity does not resolve within 12 weeks of last dose or inability to reduce corticosteroid to 10 mg or less of prednisone or equivalent per day within 12 weeks
Hyperthyroidism	3	Toxicity resolves to Grade 0-1	Toxicity does not resolve within 12 weeks of last dose or inability to reduce corticosteroid to 10 mg or less of prednisone or equivalent per day within 12 weeks
	4	Permanently discontinue	Permanently discontinue
Hypothyroidism		Therapy with pembrolizumab can be continued while thyroid replacement therapy is instituted	Therapy with pembrolizumab can be continued while thyroid replacement therapy is instituted
Infusion Reaction	2 ^b	Toxicity resolves to Grade 0-1	Permanently discontinue if toxicity develops despite adequate premedication

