5.5.2.3 Pembrolizumab

Pembrolizumab will be diluted and administered as a dose of 200 mg using a 30-minute IV infusion. Sites should target infusion timing to be as close to 30 minutes as possible. However, given the variability of infusion pumps, a window between -5 minutes and +10 minutes is permitted (i.e. infusion time is 30 minutes -5 min/+10 min). Do not co-administer other drugs through the same infusion line. Pembrolizumab infusions will be administered Q3W for up to 24 months. The instruction for use contains specific instructions for the preparation of the pembrolizumab infusion and administration of infusion solution.

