A Safety Run-in will be completed since there are no precedent data on the addition of pembrolizumab to the planned drug combinations. Treatment of the first 6 randomized subjects in each treatment arm will be staggered, with no more than 1 subject treated per week, per arm. Subjects will be monitored during the Safety Run-in Period [the first 21 days] using the protocol defined DLT criteria. In the event ≥2 subjects in up to 6 (per arm) experience DLTs, the SRC will convene to determine if subsequent subjects enrolled will require a different dose level (per **Table 2**), or if additional subjects should be enrolled at a specified dose level to further assess safety and tolerability. In the event >2 subjects in the next 6 subjects (per arm) treated experience DLTs, the SRC will reconvene to determine if the dose will be further modified for the remaining subjects to be enrolled. The SRC may convene at any time during the Safety Run-in Period to review and evaluate available safety data as warranted by emerging safety data.

Sponsor: Aduro Biotech, Inc.
Protocol Number: ADU-CL-11
Version and Date: Version 1.0, 03MAY2018

Table 2: Safety Run-in Dose Levels and Dose Reduction Table

| Dose level | pembrolizumab | epacadostat | CRS-207 |
|------------|---|-------------|---------------------|
| 1 | 200 mg | 300 mg BID | 1×10^9 CFU |
| -1 | 200 mg | 100 mg BID | 1×10^9 CFU |
| -2 | Further dose reductions will be discussed and confirmed by the SRC based on emergent safety data. | | |

Phase 2 will utilize a 2-stage design. Subjects will be randomized 1:1 into 2 treatment arms. In the first stage, once the final dose is confirmed in the Safety Run-in, a total of 13 subjects will be randomized into each arm (total 26 subjects). If the phase 2 dose is modified, at least 13 subjects will be enrolled and treated at the final dose level in each arm. If the pre-specified objective response-rate (ORR) and progression-free survival (PFS) criteria for advancement in the 2-stage design are met (≥ 1 response or median PFS ≥ 4.8 months) for an arm, an additional 14 subjects will be enrolled in that arm, for a potential total of 27 subjects per arm (up to 54 subjects total if both arms advance to stage 2).

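### SAP 6.8 labels mean pembrolizumab dose per administration as dose intensity per cycle, so missed, held or delayed cycles cannot show in it

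*SAP*

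**What the plan says.** SAP 6.8 introduces the pembrolizumab summary with this sentence: "The average dose intensity for each pembrolizumab cycle will be summarized". The unit is mg per cycle, per subject. The formula is the sum of mg received divided by the count of administrations.

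The protocol fixes both dose and interval. Section 5.5.2.3 says "Pembrolizumab will be diluted and administered as a dose of 200 mg using a 30-minute IV infusion" and "Pembrolizumab infusions will be administered Q3W for up to 24 months". Omitted doses are foreseen in section 4.3.2: "Pembrolizumab dosing may be delayed up to 2 weeks, after which time it will be considered missed", after which the subject moves on to the next scheduled dose. Table 7 in section 5.4.2 deals with pembrolizumab toxicity by holding, restarting or discontinuing and has no column for a lower dose. The two numbered safety run-in levels (SAP Table 2, levels 1 and -1) both keep 200 mg; level -2 is left to the Safety Review Committee.

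The same SAP section treats epacadostat differently. Its mean daily dose is total mg divided by the duration of epacadostat therapy, so gaps between doses lower it.

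**The concern.** Dose intensity per cycle should fall when a cycle passes without drug. Here it cannot, because the skipped cycle leaves the numerator and the denominator together. With a drug whose dose is not reduced, lower exposure arises mainly through omitted or delayed infusions, and the named metric does not register these.

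What is at stake is how the Phase 2 exposure table (Table 14.1.4.2) is read. Safety is a Phase 2 primary objective, and SAP section 9 has efficacy listed but not summarized, so safety and exposure tables carry much of the synopsis. A value near 200 mg per cycle in both arms would suggest that pembrolizumab was delivered at full planned intensity, whatever the true pattern. In the triplet arm the same table would show epacadostat falling with interruptions beside a pembrolizumab figure that does not move.

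**Working it through.** The documents report no dose-intensity value, so there is no figure to reproduce. The check applies the SAP formula to dosing histories.

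**Inputs**
- Dose 200 mg, interval 21 days: Protocol 5.5.2.3.
- Formula, total mg / administrations: SAP 6.8.
- Duration of treatment, last dose date − first dose date + 1: SAP 5.3.
- The histories (8 scheduled cycles, half-delivered infusions, carried-forward delays) are assumptions for illustration. The weeks 0 and 12 case uses the 12-week limit in Protocol Table 7.

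**Step 1: missed or held cycles.** For n completed infusions out of N scheduled, the SAP formula gives 200n / n = 200 mg for any n. Per scheduled cycle the value is 200n / N.

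| Given / scheduled | SAP formula (mg) | Per scheduled cycle (mg) | % of planned |
|---|---|---|---|
| 8 / 8 | 200 | 200 | 100 |
| 6 / 8 | 200 | 150 | 75 |
| 4 / 8 | 200 | 100 | 50 |
| 2 / 8 | 200 | 50 | 25 |
| 2 / 5 (weeks 0 and 12 only) | 200 | 400 / 5 = 80 | 40 |

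**Step 2: delays.** If every dose is late and the delay carries forward, mg per 3 weeks is 200 × 3/4 = 150 (75%) for a 1-week delay and 200 × 3/5 = 120 (60%) for a 2-week delay. The SAP formula still gives 200.

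**Step 3: what does move the metric.** Suppose one infusion is half delivered.
- 8 of 8 given: (7 × 200 + 100) / 8 = 187.5 mg.
- 6 of 8 given: (5 × 200 + 100) / 6 = 183.3 mg, against 1,100 / 8 = 137.5 mg per scheduled cycle.
- A single, half-delivered infusion: 100 mg.

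The metric thus measures how completely the given infusions were delivered.

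**Step 4: where the denominator must end.** A simple repair would use the SAP 5.3 duration, which ends on the day of the last infusion. Adding 20 days completes the last cycle: 8 on-time doses span 148 days, and (148 + 20) / 21 = 8 cycles. It still loses cycles held after the last infusion.
- Doses at cycles 1, 3, 5 and 7 of 8: 127 days, (127 + 20) / 21 = 7 cycles, 800 / 7 = 114.3 mg instead of 100.
- Doses at cycles 1 to 4, cycles 5 to 8 held and never resumed: 64 days, (64 + 20) / 21 = 4 cycles, 800 / 4 = 200 mg, the same answer as the present formula.

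Counting scheduled cycles up to the decision to discontinue, taken here to fall after the eighth scheduled dose day and before the ninth, gives 800 / 8 = 100 mg in both cases.

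**The case against.** The best defence is that this is only a naming problem in an abbreviated SAP, written for a synopsis after the sponsor had stopped CRS-207 development. Each cycle can be read as each cycle in which drug was given; the quantity is then a valid description of delivered infusions. Neither document promises relative dose intensity. SAP 6.8 also reports pembrolizumab cycle counts, CRS-207 infusion counts, duration of treatment for each drug, infusion interruptions with reasons, and by-subject administration listings. An arm that skipped many infusions would show low cycle counts for its duration.

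Most of this stands, and it limits the point. It does not rescue the label: a quantity called dose intensity in mg per cycle should respond to cycles without drug, and no planned summary sets infusions given against infusions scheduled.

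Three stronger readings are tempting, and the documents do not support them.
- *The AE rates are distorted.* They are not. SAP 8.1 divides by subject-years of safety observation, which SAP 5.3 builds from first and last treatment dates plus 30 days. Dose intensity does not enter.
- *CRS-207 has the same defect.* It does not. SAP 6.8 describes that quantity as an average volume per infusion or cycle and never as dose intensity; volume over administrations is exactly volume per infusion. Only the alternative per-cycle unit is loose.
- *Every subject will show 200 mg.* Not quite. Protocol Table 9 allows an infusion to be stopped, and the committee could set another dose at level -2. Either could move the metric; missed cycles still could not.

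**Conclusion.** The formula does not measure what its label says. It gives mean dose per administration, equal to 200 mg for completed infusions however many cycles were missed, held or delayed. In the 4-of-8 example it overstates delivered intensity twofold (200 against 100 mg per scheduled cycle). This follows by algebra from the fixed dose; the size in the actual data depends on how many infusions were omitted, which the documents do not give.

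Severity is minor. One descriptive metric is affected. The SAP plans no significance tests, efficacy endpoints and AE rates are unchanged, and a reader could reconstruct omissions from cycle counts, durations and listings. It would go too far to infer that the tolerability signal is lost: it is missing from the named metric, not from the outputs as a whole.

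**What to change.** - Compute pembrolizumab dose intensity as total mg divided by scheduled 3-week cycles from the first infusion to a stated end date. A suitable end date is the decision to discontinue pembrolizumab, or the data cutoff if treatment is ongoing. Cycles held after the last infusion then count. One form is the whole number of 21-day intervals from first infusion to end date, plus 1, with the protocol's 3-day visit window allowed for.
- Report it also as percent of the planned 200 mg every 3 weeks.
- If the present quantity is kept, call it mean dose per administration.
- For CRS-207, drop the per-cycle unit and keep volume per infusion. After Cycle 6 it is given every 6 weeks, so infusions and 3-week cycles are not interchangeable.

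The cost is one denominator, one footnote and one added row in the exposure table. Infusion records are already due in Listing 16.2.5.3. The documents do not show whether a discontinuation decision date is recorded separately for each drug. If it is not, the SAP should name a substitute, such as the end-of-treatment visit date, and note that this can run late for a subject who stopped pembrolizumab before the other drugs.
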